3.4.10 Serum benralizumab concentration

All PK samples will be collected according to the CSP Table 2. Pharmacokinetic samples will be collected before administration of IP, where applicable. Pharmacokinetic samples will also be collected at disease control if no IP administration has occurred.

The following samples will be analysed:

Double-blind treatment period:

- PK samples from participants assigned to the benralizumab treatment group

OLE period:

- PK samples at Visit 19 (Week 60) in the OLE period in all groups.

Concentration results below the lower limit of quantification (BLQ) will be set to LLOQ/2 for analysis and will be listed as <LLOQ.

Drug concentration information that would unblind the study will not be reported to investigative sites or blinded personnel until the study has been unblinded.

3.4.11 Anti-drug antibodies (ADA)

Blood samples for determination of ADA in serum will be collected as detailed in the CSP Table 2 and prior to IP administration where applicable. Anti-drug antibodies variables, such as ADA responses, will be generated and analysed as per the details in Appendix 8.2.

3.5 Safety outcome variables

Safety and tolerability will be evaluated in terms of: reported AEs (including serious adverse events [SAEs]), clinical laboratory assessments, vital signs, physical examination and 12-lead electrocardiogram (ECG).

All safety measurements will use all available data for analyses, including data from unscheduled visits and repeated measurements.

Change from baseline to each post-treatment time point where scheduled assessments were made will be calculated for relevant measurements. Safety data will be summarized by means of descriptive statistics and qualitative summaries.

The handling of partial/missing dates for AEs is detailed in Appendix 8.3. Duration of AEs will not be calculated using imputed dates and will instead be set to missing. No other safety data will be imputed.

3.5.1 Adverse Events

All AEs will be collected starting from screening (Visit 1), throughout the treatment period, and including the follow-up period.

Serious AEs will be recorded from the time the participant signs the informed consent form (ICF), throughout the duration of the study.

Any non-serious AEs with a start date later than 12 weeks after the last dose of IP will be excluded from the analysis.

Adverse events will be coded using the most recent version of the Medical Dictionary for Regulatory Activities (MedDRA) that will have been released for execution at AstraZeneca/designee per the Data Management Plan.

A per Section 9.4.3.2 of CSP, the following events are considered treatment emergent:

AEs with an onset date on or after the first dose of IP

Worsening of pre-existing events on or after first dose of IP

For the analysis, an AE will be defined as Treatment Emergent AE (TEAE) if it has an onset date on or after the first dose of IP. Applying this definition, also the worsening of pre-existing events on or after the first dose of IP will be included in the analysis as Investigators are instructed to record these as new events.

The handling of partial/missing dates for AEs is detailed in Appendix 8.3. Treatment Emergent AEs data will be categorized according to their onset date into the following study periods:

AEs in the pre-treatment period are defined as those with an onset prior to the day of first dose of study treatment.

AEs in the on-treatment period are defined as those with onset date between day of first dose of study treatment and the day of the scheduled follow-up visit or date of last dose + 12 weeks, whichever is earlier. If the upper limit is after the end of on-study period, then the upper limit is set to the end of on-study period.

AEs in the post-treatment period are defined as those with onset date after the on-treatment period defined above.

AEs in the on-study period are defined as those with onset on or after the day of first dose of study treatment.

If an AE has a missing onset date then unless the stop date of the AE indicates otherwise, this will be considered an on-treatment AE. Similarly, if an AE has a partial onset date, then unless the partial onset date or the stop date indicates otherwise, this will be considered an on-treatment AE.

AEs in the on-treatment double-blind period are defined as those with an onset date between day of first dose of study treatment and day prior to first dose of study treatment in OLE period. For participants who do not transition into OLE all the AEs in the on-treatment period are included in the on-treatment double-blind period.

AEs in the on-treatment OLE period are defined as those with an onset date between the day of first dose of study treatment in the OLE period and the day of the scheduled follow-up visit or date of last dose + 12 weeks, whichever is earlier. If the upper limit is after the end of on-study period, then the upper limit is set to the end of on-study period.

The Investigator will assess the causal relationship between IP and each AE, and answer ‘yes’ or ‘no’ to the question ‘Do you consider that there is a reasonable possibility that the event may have been caused by the investigational product?’. For SAEs, the causal relationship will also be assessed for other medication and study procedures. Note that for SAEs that could be associated with any study procedure, the causal relationship is implied as ‘yes’.

Adverse events that have missing causality (after data querying) will be assumed to be related to study drug.

The Investigator will assess the severity of each AE as “Mild”, “Moderate” or “Severe”. Adverse events that have missing severity will be assumed to be severe.

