4.2.9.1 Adverse Events

Treatment Emergent Adverse Events (TEAEs) will be summarized separately for the on-treatment, on-study, and post-treatment periods, as defined in Section [3.5.1](#). The primary period of interest for safety summaries will be the on-treatment period, unless differently specified.

Adverse events in the pre-treatment period (with start date prior to the first dose of IP) will be listed for the double-blind treatment period at primary database lock only.

Non-serious AEs with an onset date after the on-treatment period will be listed but excluded from the summaries.

All summaries will be presented by treatment group and key tables will include exposure-adjusted rates to account for any differences in follow-up if applicable.

An overall summary table will be produced showing the number, percentage, and exposure-adjusted rate of participants with at least 1 TEAE in any of the following categories; TEAEs, SAEs, AEs with outcome of death, and AEs leading to discontinuation of IP (DAEs).

The rate of TEAEs, SAEs, AEs with outcome of death and DAEs per person-years at risk will be calculated for the on-treatment period as (number of participants reporting the TEAE) / (total time with participants at risk of TEAE). For SAEs and AEs with outcome of death the rate per person-years at risk will be calculated also for the on-study period as (number of participants reporting the TEAE) / (total time with participants at risk of TEAE). The total period at risk for each participant will be the duration of the on-treatment and on-study periods as defined in Section 3.5.1. Rates will be expressed in terms of events per 100 participant-years.

The post-treatment AEs will be listed.

Treatment-emergent AEs, AEs with outcome of death, SAEs and DAEs will be presented for each treatment group for the on-treatment and on study periods by SOC and PT, including the number and percentage of participants reporting at least one event (ie, multiple occurrences of an AE for a participant will only be counted once), number of events and exposure-adjusted rates (where applicable).

A summary of the most common (frequency of >5%) TEAEs will be presented by PT.

Treatment-emergent AEs and SAEs causing discontinuation of the study treatment and SAEs causing discontinuation from the study will also be summarized.

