8.2.2 ADA and safety

Adverse events and SAEs during the study (separately for on-treatment and on-study periods) will be summarized by ADA status (treatment-emergent ADA positive, ADA negative), if enough data are available. The on-treatment and on-study periods are as defined in Section

3.5.1. AEs and SAEs will also be evaluated by causality as assessed by the Investigator. The potential impact of ADA on hypersensitivity will also be assessed.

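### As written, the on-study adverse event tables would hold only on-treatment AEs plus later SAEs, although the SAP defines the on-study period as all onsets from first dose

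*SAP*

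**What the plan says.** SAP 3.5.1 sets the periods. The on-treatment period runs from first dose to the scheduled follow-up visit or 12 weeks after the last dose, whichever comes first. The on-study period has no such limit and no restriction to serious events: "AEs in the on-study period are defined as those with onset on or after the day of first dose of study treatment". A TEAE is likewise any AE starting on or after first dose.

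Two places then promise on-study tables that are not confined to serious events:

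- SAP 4.2.9.1 says that TEAEs, deaths, SAEs and AEs leading to discontinuation "will be presented for each treatment group for the on-treatment and on study periods by SOC and PT". Its opening sentence also promises TEAE summaries for the post-treatment period.
- SAP 8.2.2, if enough data are available: "Adverse events and SAEs during the study (separately for on-treatment and on-study periods) will be summarized by ADA status".

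Two sentences take late non-serious events out again:

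- SAP 3.5.1: "Any non-serious AEs with a start date later than 12 weeks after the last dose of IP will be excluded from the analysis".
- SAP 4.2.9.1: "Non-serious AEs with an onset date after the on-treatment period will be listed but excluded from the summaries".

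SAP 3.5.1 also caps the on-treatment period, and separately the on-treatment OLE period, by a date it never defines: "then the upper limit is set to the end of on-study period".

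The hierarchy is clear: "The primary period of interest for safety summaries will be the on-treatment period, unless differently specified".

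**The concern.** The exclusions are general and the table promises are specific, and no sentence reconciles them. A programmer who follows the exclusions produces on-study tables that do not match the on-study definition. One who follows the definition breaks the exclusions. The post-treatment TEAE summary has the same problem, since under the exclusion it could hold only serious events.

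The omitted events can occur and would be collected. Protocol 4.1.2 asks participants who stop IP early to complete all visits to Week 36, and Protocol 8.3.1 collects all AEs, not only serious ones, through follow-up to last contact.

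At stake is how a supplementary table is read. A table titled as on-study TEAEs suggests a complete count whether or not IP was stopped. For non-serious events it would only repeat the on-treatment table, and the SAP does not ask for a note to say so.

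**Working it through.** The plan states no figure to reproduce on this point. The check has two parts.

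**1. What the on-study tables would contain**

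- On-study by definition: all onsets from first dose, that is, on-treatment plus post-treatment.
- Removed by 3.5.1: non-serious onsets more than 12 weeks after last dose.
- Removed by 4.2.9.1: non-serious onsets after the on-treatment period, which ends no later than last dose plus 12 weeks. This is the wider rule when the follow-up visit falls before 12 weeks (visit window ±7 days, Protocol Table 2).
- Left over: all on-treatment AEs, plus SAEs (including deaths) that start later.

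For non-serious events, then, the on-study and on-treatment tables are the same.

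**2. How much onset time is cut off for one participant**

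Inputs: dosing every 4 weeks from Week 0; double-blind follow-up to Week 36 (Protocol 4.1.2); last dose plus 12 weeks as the limit (SAP 3.5.1). For a participant with last dose at week w who does not restart IP and stays to Week 36:

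weeks omitted = max(0, 36 − (w + 12))

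| Last dose (week) | Limit (week) | Weeks omitted | Share of 36 weeks |
|---|---|---|---|
| 0 | 12 | 24 | 67% |
| 4 | 16 | 20 | 56% |
| 8 | 20 | 16 | 44% |
| 12 | 24 | 12 | 33% |
| 16 | 28 | 8 | 22% |
| 20 | 32 | 4 | 11% |
| 24 or later | 36 or later | 0 | 0% |

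**Arm level, by assumption only.** The documents give no discontinuation rate. Suppose that 10% to 30% of an arm of 50 (SAP 1.3) stop early, that their last doses are spread evenly over Weeks 0, 4, …, 28, and that all stay to Week 36. The mean omitted time per stopper is (24 + 20 + 16 + 12 + 8 + 4 + 0 + 0)/8 = 84/8 = 10.5 weeks. With 5 to 15 stoppers that is 5 × 10.5 = 52.5 to 15 × 10.5 = 157.5 person-weeks. Out of 50 × 36 = 1800 this is 2.9% to 8.75%. If only half of the stoppers stay, and the others leave within 12 weeks of their last dose, the omitted person-weeks halve.

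These are shares of observation time. They do not measure lost events or percentages: 4.2.9.1 counts a participant once per event, so someone who had the same event earlier already appears in the percentage.

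**The case against.** The strongest reply is that the cut-off is deliberate. It is stated twice in plain words, and it matches the protocol's follow-up visit at 12 weeks after the last dose. The safety estimand in SAP Table 8 is an on-treatment one. The rate paragraph points the same way, because it adds on-study rates only for serious outcomes: "For SAEs and AEs with outcome of death the rate per person-years at risk will be calculated also for the on-study period". On this view the specific exclusion governs the list of tables, the on-study tables were always meant as on-treatment events plus later SAEs, and only the label is wrong. The omitted events still appear in listings, and the ADA table is conditional and descriptive.

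Much of this stands. The cut-off may well be intended, and limiting late reporting to serious events is a legitimate choice. But the SOC/PT sentence and 8.2.2 name TEAEs or AEs, not only SAEs, for a period defined without that limit. If the cut-off is intended, those sentences or the titles have to change. Listings do not give incidence by arm.

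Some stronger readings are not supported by the documents:

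- *Biased on-study rates or a distorted comparison between arms.* The SOC/PT sentence mentions exposure-adjusted rates where applicable, but on-study person-year rates are specified only for SAEs and deaths, which the exclusions do not touch.
- *Lost or concealed events.* SAP 4.2.9.1 says that they are listed. That sits awkwardly with exclusion from the analysis in 3.5.1, but the data are shown.
- *An undeclared departure from the protocol.* The protocol's safety section does not split AEs into on-treatment and on-study periods, so the silence of SAP Section 6 carries little weight.
- *Two thirds of follow-up missing.* That figure applies only to a participant who takes the Week 0 dose alone and then stays to Week 36.

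**Conclusion.** The point holds as an internal contradiction in the SAP and is minor. Read as written, the on-study TEAE tables in 4.2.9.1 and the on-study AE tables by ADA status in 8.2.2 would omit non-serious AEs that start after the on-treatment period.

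The size per participant ranges from 24 of 36 weeks of onset time to none, on the assumptions that the participant stays to Week 36, does not restart IP, and has the limit at last dose plus 12 weeks. A follow-up visit held up to 7 days early could add at most one week. The arm-level effect is unknown. It is probably small, since only early stoppers who remain in follow-up contribute.

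Only supplementary descriptive tables are affected. No hypothesis test, on-treatment result or specified on-study rate changes.

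**What to change.** Choose one of two options before unblinding.

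1. *Make the tables match the definition.* Limit both exclusion sentences to the on-treatment summaries, for example: *The cut-off for late non-serious events applies to on-treatment summaries only; on-study and post-treatment summaries count every event in their period.* On-treatment plus post-treatment then adds up to on-study, and no on-treatment table changes.
2. *Keep the cut-off and say so.* Restrict the on-study and post-treatment tables in 4.2.9.1 and 8.2.2 to SAEs and deaths, or title the on-study tables *On-treatment TEAEs plus later SAEs*.

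Under either option, define the end of the on-study period as last contact (SAP 3.1.6), and apply the double-blind cut-off of SAP 3.1.2 separately for the primary CSR. That definition also works for the cap on the on-treatment OLE period.

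The cost is two or three sentences and one definition, with data already collected and tables already planned. Option 1 has a small downside: late events may be confounded by changed background therapy, which Protocol 7.1.1 allows after IP is stopped. That is a good reason to keep on-treatment as the primary safety period. Option 2 avoids this but gives no table of late non-serious AEs.

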3.5.2 Clinical laboratory variables

Blood and urine samples for determination of clinical chemistry, haematology and urinalysis parameters will be taken at the times detailed in the CSP Table 2 during the double-blind and OLE periods. The parameters outlined in the CSP Table 7 will be collected. Local laboratory results will not be included in the analysis.

In summaries, figures, and listings, laboratory results and normal ranges will be presented in System International (SI) units. Eosinophil data will be presented in both SI and conventional units (cells/ μ L) in summaries.

Changes in haematology and clinical chemistry variables between baseline and each post-baseline assessment will be calculated. For values recorded with a leading greater than or less than (‘>’, ‘<’) symbol, the reported numeric value will be used for analysis and the value with the symbol will be included in the listings, unless otherwise specified. For example, a value of <0.01 will be analysed as 0.01 and listed as <0.01.

Absolute values will be compared to the relevant reference range and classified as low (below range), normal (within range or on limits) or high (above range). The central reference ranges will be used for laboratory variables. All absolute values falling outside the reference ranges will be flagged.

Maximum or minimum value post-baseline will be calculated over the entire post-baseline period, including the post-treatment period. The maximum or minimum value post-baseline will be calculated over the double-blind period for all participants and during the OLE period for the participants who are included in the OLE period.

For the liver function tests aspartate aminotransferase (AST), alanine aminotransferase (ALT), alkaline phosphatase (ALP), gamma-GT (GGT) and total bilirubin (TBL), the multiple of the central laboratory upper limit of the normal (ULN) range will be calculated for each data point.

$$\text{Multiple} = \text{Value} / \text{ULN}$$

That is, if the ALT value was 72 IU/L (ULN=36) then the multiple would be 2.

Participants who meet any of the following criteria at any point during the study will be flagged:

AST \geq 3x ULN

ALT \geq 3x ULN

TBL \geq 2xULN

Urinalysis data with qualitative results will be categorized as negative (0), positive (+), or strongly positive (++, +++, or >++) at each timepoint.

3.5.3 Vital signs and physical examination

Pre-dose vital signs (pulse, systolic blood pressure, diastolic blood pressure, respiration rate, body temperature) will be obtained in accordance with the schedule provided in the CSP Table 2.

Body temperature will be measured in Celsius in accordance with local standards; weight will be recorded in kilograms.

Physical examinations (complete or brief), including height and weight, will be conducted in accordance with the schedule provided in the CSP Table 2. Baseline measurements will be assessed at screening (Visit 1) or the randomization visit (Visit 2) before first dose of IP. Any new findings or aggravated existing abnormalities, judged as clinically significant by the Investigator, will be reported as an AE as described in the CSP Section 8.3.5.

The complete physical examination will include an assessment of the following: height and weight, general appearance, skin, head and neck (including eyes, ears, nose, mouth, and throat), lymph nodes, abdomen, musculoskeletal (including spine and extremities), cardiovascular, respiratory, and neurological systems.

The brief physical examination will include an assessment of the following: weight, general appearance, skin, abdomen, cardiovascular, and respiratory system. For the brief physical examination, only information on whether the assessment was performed or not is to be recorded. Weight measurements will be performed in light clothing and without shoes and will be recorded in kilograms.

Body Mass Index will be calculated from the height and weight as follows:

$$BMI \text{ (kg/m}^2\text{)} = \text{Weight (kg)} / (\text{Height (m)})^2$$

Changes in vital signs variables, weight and BMI between baseline and each subsequent scheduled assessment will be calculated.

Absolute values will be compared to the reference ranges in Table 6 and classified as low (below range), normal (within range or on limits) or high (above range). All values (absolute and change) falling outside the reference ranges will be flagged.

Table 6 **Vital signs reference ranges**

Parameter	Standard unit	Lower limit	Upper limit
Diastolic Blood Pressure	mmHg	60	120
Systolic Blood Pressure	mmHg	100	160
Pulse Rate	Beats/min	40	120
Respiratory Rate	Breaths/min	8	28
Body Temperature	Celsius	36.5	38
Weight	kg	35	200

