#### **9.4.3.4 Vital Signs**

Details of all vital signs analyses will be provided in the SAP. As an overview, descriptive statistics will be presented for observed and change from baseline values for all vital sign parameters, which include the continuous measures: systolic blood pressure, diastolic blood pressure, pulse rate, respiration rate and body temperature.

For each treatment group:

- The parameters will be summarized at each scheduled post-baseline visit and will include: number of available observations, mean, standard deviation, median, minimum and maximum, and quartiles where more appropriate.
- The number and percentage of participants falling into specific vital signs categories (defined in the SAP) will be presented at each scheduled post-baseline visit in a frequency table.
- Changes in vital signs measurements will be examined at each scheduled post-baseline visit and clinically noteworthy values observed during the study (defined in the SAP) will be presented in a frequency table.

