4.2.9.3 Vital signs and physical examination

For vital signs data, descriptive statistics for absolute value, change from baseline and percent change from baseline will be presented for each treatment group by scheduled visit and separately for the double-blind period and the OLE period. Summary statistics for continuous variables will include n, mean, standard deviation, median, minimum value and maximum value.

All vital sign and physical examination data will be listed.

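### SAP 3.5.3 flags vital-sign changes against absolute-value limits, so the change flag carries no information; separately, the SAP omits the vital-sign frequency tables the protocol promises

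*SAP*

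**What the plan says.** SAP 3.5.3 calculates changes from baseline in vital signs, weight and BMI. It classifies absolute values as low, normal or high against Table 6, with values on a limit counted as normal. It then adds: "All values (absolute and change) falling outside the reference ranges will be flagged". Table 6 gives one lower and one upper limit for each of six parameters; the systolic row, for example, reads "Systolic Blood Pressure mmHg 100 160". Neither document gives any limits for change.

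Protocol 9.4.3.4 makes two tabulation promises. Participants falling into vital-sign categories, to be set out in the SAP, will be counted at each scheduled post-baseline visit. Changes will also be examined, and "clinically noteworthy values observed during the study (defined in the SAP) will be presented in a frequency table". Protocol 9.4.3.5 repeats the second promise for body weight.

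SAP 4.2.9.3 plans descriptive statistics for the value, the change and the percent change, by arm and visit, and then says: "All vital sign and physical examination data will be listed". It has no frequency table. SAP Section 1 says that changes from the protocol will be described in Section 6, and Section 6 is silent on this one.

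**The concern.** A range built for absolute values cannot screen differences. A stable systolic pressure has a change of 0 mmHg, which is below 100 mmHg and so counts as out of range. A flag that is almost always on cannot point a reader to a participant or separate the arms.

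The missing tables are a second and separate gap. Vital signs, including body weight, belong to the safety objective in both documents, and all participants take oral corticosteroids from Visit 2 (protocol 4.1.2), so blood pressure and weight are of interest. The protocol left the noteworthy-value criteria to the SAP. If these are first set after unblinding, they are post hoc.

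**Working it through.** The documents state no figure to reproduce here, so the check applies the rule literally.

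**Inputs.** Limits L and U come from SAP Table 6. Change is the post-baseline value minus the baseline value (SAP 3.1.3). The documents give no standard deviation for change. The ranges below are assumptions, with the mean change m set at 0 or at +0.5 SD.

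**Step 1: no assumption needed.** A change d is flagged if d < L or d > U. All six L are positive, so d = 0 and every d < 0 are flagged. The smallest change that is not flagged is +L. The largest change possible between two in-range values is U − L. Where U − L < L, every change between two in-range values is flagged.

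**Step 2: size, under the assumed SDs.** With change taken as normal with mean m and SD s:

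P(flagged) = 1 − [Φ((U − m)/s) − Φ((L − m)/s)]

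Two worked cases:
- Systolic, s = 30, m = 15: 1 − [Φ(4.83) − Φ(2.83)] = 0.998.
- Respiratory rate, s = 5, m = 2.5: 1 − [Φ(5.1) − Φ(1.1)] = 0.864.

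| Parameter | L to U | Smallest unflagged change | U − L | Assumed SD | P(flagged) |
|---|---|---|---|---|---|
| Diastolic (mmHg) | 60–120 | +60 | 60 | 5–20 | 99.4–100% |
| Systolic (mmHg) | 100–160 | +100 | 60 | 10–30 | 99.8–100% |
| Pulse (/min) | 40–120 | +40 | 80 | 5–20 | 93.3–100% |
| Respiratory rate (/min) | 8–28 | +8 | 20 | 1–5 | 86.4–100% |
| Temperature (°C) | 36.5–38 | +36.5 | 1.5 | 0.3–1.0 | 100% |
| Weight (kg) | 35–200 | +35 | 165 | 2–10 | 99.9–100% |

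The low ends for pulse and respiratory rate arise only at the largest SDs (20/min and 5/min). At SDs of 10/min and 2/min the rate is at least 99.98%. For systolic pressure (60 < 100) and temperature (1.5 < 36.5), no change between two in-range values can escape.

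The rule is also inverted. An unchanged diastolic pressure is flagged, while a rise of 60 to 120 mmHg is not. BMI change is calculated as well, but Table 6 has no BMI row.

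**Step 3: promise against plan.**
- Protocol 9.4.3.4, counts by vital-sign category at each visit: SAP 3.5.3 defines low, normal and high classes, but SAP 4.2.9.3 has no table that uses them.
- Protocol 9.4.3.4 and 9.4.3.5, frequency tables of noteworthy vital-sign and weight values: the SAP labels no criteria as noteworthy and plans no table.
- By contrast, SAP 3.5.2 flags absolute laboratory values only, and SAP 4.2.9.2 plans shift tables of their low, normal and high classes.

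**The case against.** The strongest reply is that the reference to change is a drafting slip. The sentence before it ties Table 6 to absolute values, the laboratory rule covers absolute values only, and a programmer would hardly implement a rule that calls a zero temperature change low. In practice the change flag might simply be dropped. That is plausible, but the text says otherwise and offers no other limits, so the programmer would have to guess.

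Three stronger readings are tempting, and the documents do not support them.

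- A reader might infer that large changes would be hidden. They would not. SAP 4.2.9.3 reports change by arm and visit with minimum and maximum, and all vital-sign data are listed. Protocol 8.3.5 makes a deterioration from baseline an adverse event when it is serious, leads to stopping the investigational product or is judged clinically relevant. No planned summary is built from the flag.
- A reader might infer that every change record is flagged for every parameter. Under wide assumed SDs, some rises in pulse and respiratory rate escape.
- A reader might infer that the protocol promised limits for change. It promises noteworthy values, and the classes in Table 6 could arguably supply part of that definition. What is plainly missing is the tables.

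**Conclusion.** Wrong as written, with small consequences. Read literally, the change flag fires for no change, for every decrease and for nearly all plausible increases, so it is uninformative. The result for zero change and decreases follows from the positive lower limits alone. The percentages for increases rest on the assumed SDs and a normal distribution: at least 99.4% for blood pressure, temperature and weight, and down to 93.3% for pulse and 86.4% for respiratory rate at the widest SDs. The flag on absolute values works as intended.

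The missing frequency tables are the firmer of the two defects, because they rest only on setting protocol 9.4.3.4 and 9.4.3.5 beside SAP 4.2.9.3 and Section 6. Neither defect affects an efficacy estimate or the type I error rate.

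**What to change.** 1. In SAP 3.5.3, remove the reference to change so that the flag covers absolute values only, as in SAP 3.5.2. If a change flag is wanted, the sponsor should pre-specify separate limits for each parameter before unblinding.
2. In SAP 4.2.9.3, add by-arm frequency tables of the Table 6 low, normal and high classes at each scheduled post-baseline visit, and of noteworthy vital-sign and weight values under whatever criteria the sponsor defines. If any of these tables is not wanted, record its removal in SAP Section 6.

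The cost is one sentence and one or two safety outputs, with no new data collection.
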